3.3.3. Acceptability and beverage consumption adherence

Beverage acceptance was assessed through a sensory analysis once a week for 4 weeks using a 7-point hedonic scale, considering the characteristics of color, odor, flavor, mouthfeel, aftertaste, and overall appearance. The scoring system was as follows: 1 = I dislike it a lot, 2 = I dislike it moderately, 3 = I dislike it a little, 4 = I neither like it nor dislike it, 5 = I like it a little, 6 = I like it moderately, and 7 = I like it a lot. To conduct this assessment, participants were sent a Google Form via WhatsApp. This form also included a section to indicate any other sensations they perceived when consuming the beverage, as well as their percentage of daily consumption of the beverage, and thus assess attachment.

Beverage acceptance is assessed using the hedonic scale, and the score is evaluated whether the score is maintained over the duration of the trial. The feedback provided by participants allows adjustments to improve beverage acceptance, if necessary.

3.3.4. Gastrointestinal tolerability due to consumption of the beverage.

Once a week for the 4 weeks of the trial, participants completed a gastrointestinal tolerability assessment form as proposed by De Luis *et al.* (2015), where participants indicated the presence or absence of gastrointestinal symptoms such as nausea, regurgitation, vomiting, constipation, diarrhea, flatulence, and abdominal pain. These symptoms were assessed using 5 points where: 0=absent symptom, 1=symptom present but not bothersome, 2=annoying symptom but does not interfere with daily activities or sleep, 3=a symptom present and bothersome but does interfere with daily activities and sleep, and 4=a symptom present that requires medical attention.

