1. INTRODUCTION

When developing foods with potential health benefits, it is necessary to evaluate their acceptability and tolerability to determine whether the product will be consumed by the intended population. (Yang & Lee, 2018), In addition to ensuring that its consumption does not compromise the consumer's health, these tests allow the developer to make the necessary modifications to increase the likelihood of consumption.

The acceptability of a product can be studied through surveys or interviews and the way to apply these resources is through sensory tests oriented to the consumer, these tests allow to obtain information about the aspects that are liked and disliked about the product in question (Ramírez-Nava, 2012). To achieve this, sensory analysis is used, which is defined as the scientific discipline used to measure, identify and interpret food characteristics perceived by the senses of sight, smell, taste, touch and hearing (Lawless & Heymann, 2010). Among consumer-oriented tests, there are two main ones: preference tests and acceptance tests. In preference tests, consumers are asked to indicate which sample they prefer. While in acceptance tests, consumers are presented with the products and asked to indicate their level of liking them on a scale that can be 3, 5, 7, and 9 points (Sharif *et al.*, 2017). Acceptance tests are often used to compare two or more products or used on a single product to measure the level of liking.

Pregnancy is a stage that is marked by physiological changes related to hormones that modify sensory perception (Muluh *et al.*, 2024), mainly affecting taste (Choo & Dando, 2017) and smell (Haddad-Tóvolli *et al.*, 2023); However, this has been very little studied and most of the knowledge on the subject is empirical (Köhlble *et al.*, 2001), but it has now begun to be studied as the work conducted by Matsuda *et al.* (2024) who have suggested that oxytocin has an effect on the olfactory sensitivity of pregnant women, meanwhile Muluh *et al.* (2024) found moderate evidence of sensory changes during pregnancy, such as a reduction in the ability to identify odors and changes in the perception of the intensity of odors and hedonic responses to flavors.

The proposed beverage to be evaluated is made entirely from natural compounds, which in theory should not cause gastrointestinal intolerance effects, but to reaffirm this in the

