2.2. Specific objectives

- To evaluate the acceptability of the beverage by sensory analysis in a 4-week trial with a 7-point hedonic scale.
- Determine the tolerability of the beverage by the presence of gastrointestinal symptoms.
- Evaluate biochemical indicators, blood pressure and general urine test before and after the beverage consumption trial.

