3. MATERIAL AND METHODS

A 4-week phase I pilot trial was conducted in 10 women in their second trimester of pregnancy, who consumed a daily dose of *H. sabdariffa* beverage. Acceptability and tolerability were assessed. Blood pressure, urinalysis, and blood biomarkers of glucose, cholesterol, triglycerides, and creatinine were also measured.

Figure 1 presents the experimental diagram of the beverage acceptability and tolerability test.

[figure not shown]

Figure 1. Experimental diagram of the acceptability and tolerability test of a beverage with *Hibiscus sabdariffa* L.

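### As section 3.3.3 describes it, the weekly form has no item that clearly rates liking of the beverage as a whole, so acceptance is not measured directly

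*Protocol*

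**What the plan says.** Protocol section 2.2 lists as its first specific objective: "To evaluate the acceptability of the beverage by sensory analysis in a 4-week trial with a 7-point hedonic scale".

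Section 3.3.3 describes the measurement: "Beverage acceptance was assessed through a sensory analysis once a week for 4 weeks using a 7-point hedonic scale". It names the items that each participant scores in these words: "considering the characteristics of color, odor, flavor, mouthfeel, aftertaste, and overall appearance". Of the rest of the online form it says: "This form also included a section to indicate any other sensations they perceived when consuming the beverage, as well as their percentage of daily consumption". The consumption percentage is there to assess adherence.

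The same section then states how acceptance is judged: "Beverage acceptance is assessed using the hedonic scale, and the score is evaluated whether the score is maintained over the duration of the trial".

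The Introduction separates preference tests from acceptance tests. It describes the latter as tests in which "consumers are presented with the products and asked to indicate their level of liking them on a scale".

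**The concern.** The Introduction's acceptance test rates the product. The items listed in section 3.3.3 rate properties of the product. The criterion in section 3.3.3 is worded in the singular, as if one score stood for acceptance, but six are listed each week and none is clearly a rating of the whole drink.

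The two kinds of rating answer different questions. Attribute ratings show what to change. A whole-product rating shows whether women like the drink they are asked to take every day. The Introduction wants to know whether the intended population will consume the product, and it treats acceptability as something to learn before a longer randomized trial. If the whole-product question was not asked, the pilot can describe liking of each attribute, but acceptance of the drink has to be inferred from them.

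This is a matter of data collection. An analysis plan can define a summary of the six attributes, but it cannot supply a rating that was never collected.

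**Working it through.** The protocol gives no figure to reproduce here. The sample size is one of convenience, and no acceptance threshold is stated. The check is therefore a reading of the sections against each other, with a count for the cost of the remedy.

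**Step 1: what each listed item rates**

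| Content of the weekly form (section 3.3.3) | Object rated | Rates liking of the drink as a whole? |
|---|---|---|
| Color, odor, flavor, mouthfeel, aftertaste | One sensory property each | No |
| Overall appearance | As worded, how the drink looks | Not as worded; possible if it is a loose translation |
| Other sensations | Free comment | No |
| Percentage of daily consumption | Amount drunk (adherence) | No; it is not a liking score |

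**Step 2: what the protocol needs**

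- Section 2.2 asks for acceptability of the beverage on a 7-point hedonic scale.
- The Introduction says that an acceptance test records liking of the product.
- Section 3.3.3 says "Beverage acceptance is assessed using the hedonic scale, and the score is evaluated" for being maintained over the trial.

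All three are met directly by a weekly rating of the whole drink. None of the items in Step 1 clearly provides one. The singular *score* could mean the hedonic score of each attribute taken in turn. On that reading the maintenance criterion can be applied six times, once per attribute, but it is then a statement about attributes.

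**Step 3: what one added item costs**

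Inputs: 6 rated items, 4 weekly forms (section 3.3.3) and 10 women (section 3).

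- Hedonic items per form: 6 + 1 = 7.
- Added ratings per woman: 1 × 4 = 4.
- Added ratings in all: 4 × 10 = 40.

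The result is one overall score per woman per week, to which the stated maintenance criterion applies directly.

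**The case against.** **The form itself is not shown.** Section 3.3.3 is a summary, and its English reads as a translation: it writes *attachment* for what its heading calls adherence. *Overall appearance* comes last in the list, after color has been rated separately, and may render a global item. This stands. It is why the point is limited to what the protocol describes and why the first step is to check the form. It does not remove the need to act, because the text would still have to be corrected if the item was global.

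**Attribute ratings suit the purpose.** The Introduction values learning which aspects are liked and disliked, and section 3.3.3 uses the feedback to adjust the beverage. This also stands, and the ratings should be kept. They help to explain acceptance but do not replace a rating of it.

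**The choice of summary score belongs in an analysis plan.** Agreed. That no summary, time point or threshold is designated is not part of this point. Only the possible absence of the item is.

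**The form already records consumption.** That is a useful whole-product signal, but a woman may finish a supplied dose without liking it.

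A reader might go further and infer that the trial cannot answer its first objective, that a favorable attribute could be picked, or that an average could hide a disliked flavor. The documents do not support this. The protocol proposes no averaging across attributes and no acceptable-or-not verdict. Six separately reported attributes would show a disliked flavor directly. The four weekly ratings are described as one time course and not as rival endpoints. Counts of possible means or invented rating profiles are therefore no evidence of harm.

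**Conclusion.** The point holds in a limited form. As section 3.3.3 is written, no item clearly measures liking of the beverage as a whole, although the Introduction's description of an acceptance test calls for such a rating and the acceptance criterion in section 3.3.3 fits one most naturally. The attribute ratings support reformulation and measure acceptance only indirectly.

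The effect is moderate and cannot be put as a number. No sample size, power or error rate in the protocol changes. What changes is how far the conclusion on the first specific objective can reach: liking of attributes, or liking of the drink. In a convenience pilot of 10 women this does not invalidate the study.

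The conclusion assumes that section 3.3.3 lists the rated items completely and that *overall appearance* was put to participants as a visual attribute. If the form shows a global liking question, only a wording correction remains.

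**What to change.** 1. Check *overall appearance* against the form sent to participants. If it asked for liking of the whole drink, reword section 3.3.3 to say so and name that item as the acceptability measure, with the other five ratings as diagnostics.
2. If it did not, add one weekly item on the same 7-point scale: *Overall, how much do you like this beverage?* Use its weekly scores, including whether they are maintained over the 4 weeks, as the acceptability measure. This keeps the protocol's own criterion, which a single week-4 score would displace. Keep the six attribute ratings as diagnostics for reformulation.
3. The protocol is written in the past tense, so collection may be over. In that case, and if no global item was asked, report all six attributes separately, with no selected or averaged headline. Limit the conclusion to attribute-level liking, and put the overall item on the form for the planned randomized trial.

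The cost of step 2 is one more question on each weekly form and a sentence or two in section 3.3.3. Steps 1 and 3 need only a check of the form and care in wording. The drawback of step 3 is that the pilot itself would still lack a direct measure of overall liking.

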acceptability test, a gastrointestinal tolerability questionnaire was included evaluating the presence or absence of symptoms such as nausea, regurgitation, vomiting, diarrhea, constipation and flatulence. (De Luis *et al.*, 2015).

In this work, a phase I pilot test was carried out, which consists of testing on a smaller scale the execution logistics planned for a higher-level project and thereby reducing the probability of errors in future studies (Díaz-Muñoz *et al.*, 2020). This work was approved by the Research Ethics Committee of the Biotic Products Development Center of the National Polytechnic Institute.

The study evaluated the gastrointestinal acceptability and tolerability of the proposed beverage developed to help control hypertensive disorders associated with pregnancy. Indicators such as blood pressure, blood markers of glucose, cholesterol, triglycerides and creatinine, and general urine test were also assessed. This trial was conducted on pregnant women, because this is the group to which the drink is directed and at this stage physiological changes occur that modify the sensory perception of food (Matsuda *et al.*, 2024), This is why it is important to conduct it in this group. This trial aims to lay the groundwork for defining the logistics used in a double-blind, randomized, controlled clinical trial in which the beverage will be given for a longer period of time. This is why it is important to know the acceptability of the beverage, in case it is necessary to make changes to the beverage that allow for increased consumption (Lawless & Heymann, 2010).

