3.3.2. Participants selection

Because this was a phase 1 pilot study, where participants were self-controlled, with marker measurements taken before starting to consume the beverage and at the end of the 4-week treatment period, the sample size was based on convenience. All women who met the inclusion criteria and did not meet the exclusion criteria were invited to participate. At least ten pregnant women were recruited through the consultation of PhD. [name], a specialist in obstetrics and gynecology and maternal-fetal medicine at the "MEDOMAI" Comprehensive Health Services Clinic located in Cuernavaca, Morelos, México.

Participants were selected according to the following criteria:

Inclusion criteria

- Pregnant women aged 18 to 35
- Those in their second trimester of pregnancy (14 – 28 gestation weeks)
- Blood pressure <140/90 mmHg

Exclusion criteria

- Multiple or high-risk pregnancy
- Having suffered from a hypertensive disorder in previous pregnancies

- Having chronic non-communicable diseases such as diabetes mellitus, cardiovascular disease, cancer, and chronic kidney disease
- Body Mass Index $\geq 32 \text{ kg/m}^2$

Elimination criteria

- Develop any pregnancy complications that prevent you from consuming the beverage and/or attending the measurements
- Deciding of your own volition to withdraw from the study

The patient records were reviewed to select patients who met the criteria for pregnancy weeks and age. They were contacted by telephone, where their medical history was taken to confirm that they met the remaining criteria. The procedures to be performed and how to prepare the beverage were explained in detail. In this conversation, the candidates were asked about their interest in participating and the date they should arrive to sign the informed consent form, receive the powdered doses to prepare the beverage along with its preparation instructions, and perform blood pressure measurements, biochemical indicators, and provide a urine sample.

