3.3.5. Blood pressure, urinalysis and biochemical markers

Blood pressure, urinalysis, and biochemical indicators of serum glucose, cholesterol, triglycerides, and creatinine were measured before the start of the trial and after the four weeks of consumption of the beverage were completed, to compare these parameters before and after treatment. The measurements and blood samples were taken by trained and experienced personnel. Blood pressure was measured using a noninvasive technique using the Korotkoff auscultation method.

Blood samples were obtained by puncture in the antecubital region of the participants' non-dominant arm, using sterile, disposable materials. Blood was placed in anticoagulant-free tubes for clinical chemistry, extracting 6 ml of blood. These tubes were kept refrigerated until the determinations were performed in the Biomarker Measurement Laboratory of the Biotic Product Development Center by personnel from the Department of Nutrition and Functional Foods, who are trained and experienced in sample collection and processing. Blood chemistry was measured using the Spinlab series 5-5312 semi-automated turbidimetry equipment for clinical chemistry.

The biological materials were used only for the aforementioned tests and were kept refrigerated until their disposal as Biologically Infectious Hazardous Waste (BIHW) in accordance with Mexican Official Standard NOM-087-SEMARNAT-SSA1-2002. The

results of the biochemical indicators were reported in writing to the participants, who received free medical and nutritional guidance, if necessary.

The general urine test was performed by the Jacobo Curiel external clinical analysis laboratory in Cuernavaca, Morelos. Participants submitted their samples to the "MEDOMAI" clinic on the indicated date, and the samples were then transferred to the external laboratory.

The researchers of this protocol declare that there is no conflict of interest and that the objective is to generate knowledge that allows us to evaluate the effect of a beverage with *H. sabdariffa*, which can be used in the prevention and/or treatment of hypertensive disorders associated with pregnancy, as well as to determine its degree of gastrointestinal acceptability and tolerability.

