4. SCHEDULE OF ACTIVITIES

Activity	2024				
	March	April	May	June	July
Information meeting with potential participants	X	X			
Interviews to verify inclusion criteria		X			
Participants selection		X			
Measurement of blood pressure and biochemical indicators before the test.		X			
Beverage acceptability and tolerability test			X		
Measurement of blood pressure and biochemical indicators after the test			X		
Analysis of results			X	X	
Preparation and submission of the report to the Research Ethics Committee					X

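### With symptom forms only during the four consumption weeks and no control group, the counts describe symptoms during consumption, not symptoms due to the beverage

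*Protocol*

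**What the plan says.** The Introduction of the protocol gives the symptom form its purpose. Of the drink, which has only natural ingredients, it says: "which in theory should not cause gastrointestinal intolerance effects, but to reaffirm this in the" (the sentence goes on to name the test of acceptability). The instrument added for this purpose is then described: "a gastrointestinal tolerability questionnaire was included evaluating the presence or absence of symptoms". The heading of section 3.3.4 uses the same causal language: "Gastrointestinal tolerability due to consumption of the beverage". The objective in section 2.2 is descriptive: "Determine the tolerability of the beverage by the presence of gastrointestinal symptoms".

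On timing, section 3.3.4 says: "Once a week for the 4 weeks of the trial, participants completed a gastrointestinal tolerability assessment form". Each symptom is graded 0 to 4.

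The pre-dose visit is described in three places, none of which includes symptoms:

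- Section 3.3.2: besides signing consent and receiving the powder, the women are to "perform blood pressure measurements, biochemical indicators, and provide a urine sample".
- Section 3.3.5: blood pressure, urinalysis and biochemistry "were measured before the start of the trial and after the four weeks of consumption of the beverage were completed".
- Section 4 lists "Measurement of blood pressure and biochemical indicators before the test" in April and marks the acceptability and tolerability test in May only.

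Section 3.3.2 calls the participants self-controlled, but ties this to marker measurements before and after. Section 3 describes one group of 10 women.

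**The concern.** The form is asked to support a statement about what the drink causes. That needs a comparison, either with the same woman before the drink or with women not taking it. The plan has such a comparison for blood pressure, blood markers and urine, but not for symptoms. A pre-existing symptom and one that began on the drink would be recorded in the same way on the form as described.

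The attribution of any non-zero count is at stake. Background symptoms raise the count, so the bias mostly works against the beverage. A low count still supports tolerability as an upper bound, provided the drink does not itself relieve symptoms. Since the pilot is meant to prepare a randomized trial, a count read as caused by the drink could carry forward into that trial's planning. The missing baseline is a matter of data collection, so no later analysis can recover it.

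**Working it through.** **No figure to reproduce.** The sample of 10 is one of convenience (section 3.3.2), and no background symptom rate is given. The check is a comparison of the text, followed by illustrations under assumed rates.

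**Step 1. Which outcomes have a before-value?**

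| Outcome | Before first dose | During or after |
|---|---|---|
| Blood pressure, biochemistry, urine | Yes (3.3.2, 3.3.5) | Yes, after 4 weeks (3.3.5) |
| Gastrointestinal symptoms | None described | Weekly, weeks 1 to 4 (3.3.4) |

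The before/after objective in section 2.2 and the pairwise analysis in section 3.1 cover only indicators measured before and after, so they do not reach symptoms. The telephone medical history in section 3.3.2 is described as an eligibility check, not as a graded symptom record.

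**Step 2. How often would a drink with no effect produce reports?** Let b be the assumed proportion of women who would report any listed symptom over the four weeks without the drink. With n = 10 independent women, the expected count is 10b and P(X ≥ 1) = 1 − (1 − b)^10. P(X ≥ 3) is the binomial tail.

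| b (assumed) | Expected women | P(at least 1) | P(at least 3) |
|---|---|---|---|
| 10% | 1 | 0.651 | 0.070 |
| 20% | 2 | 0.893 | 0.322 |
| 30% | 3 | 0.972 | 0.617 |

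b mixes symptoms present beforehand with unrelated symptoms that arise during the four weeks. A baseline form identifies only the first kind, so these figures are not the amount that it would remove.

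**Step 3. What can a baseline form do?** The answer depends on how it is used. Assume no beverage effect, a 20% weekly symptom rate and independent weeks.

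- Any symptom in weeks 1 to 4: 1 − 0.8^4 = 0.590, or 5.9 of 10 women.
- Symptom-free in the baseline week, then any symptom in weeks 1 to 4: 0.8 × 0.590 = 0.472, or 4.7 of 10 women.
- One week against one week: 10 × 0.2 = 2 women expected at baseline and 2 in each later week, an expected difference of 0.

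Setting one baseline week against any of four later weeks would thus label 4.7 of 10 women as new cases on a drink that does nothing. At the other extreme, a fully persistent symptom of unchanged grade is removed completely under either comparison. Equal windows avoid the inflation.

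**Step 4. What would remain uncertain?**

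- Exact two-sided 95% limits (Clopper-Pearson): 0/10 gives 0 to 1 − 0.025^(1/10) = 30.8%; 3/10 gives 6.7% to 65.2%.
- An exact paired (McNemar) test with all discordant women in one direction gives P = 2 × 0.5^5 = 0.0625 for five and 2 × 0.5^6 = 0.031 for six. At least six of the 10 women would have to change the same way to reach P < 0.05, so the comparison should be descriptive.

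**The case against.** The strongest reply is that this is a small descriptive pilot and says so. The objective in section 2.2 asks only whether symptoms are present, no causal symptom analysis is planned, and controlled attribution belongs to the later randomized trial. The causal language amounts to one hedged sentence in the Introduction and one heading. A bias against the product is also the cautious direction for a first tolerability screen in pregnant women. All of this stands, and it limits the point to attribution. It does not remove the point, because the protocol itself writes the causal purpose and the form as scheduled cannot serve it.

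Three stronger readings are tempting, but the documents do not support them:

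- A reader might infer that the protocol counts pre-existing symptoms as beverage symptoms. It states no such rule. The form comes from a cited study and is not reproduced, so whether it asks about onset is unknown. The lack of a pre-dose form does not depend on this.
- A reader might infer that a harmless drink would fail the test. The protocol sets no pass or fail threshold.
- A reader might take 65% to 97% as the error that a baseline form would correct. As shown above, it is not.

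It can also be said that the protocol reports the trial in the past tense and its schedule ends in July 2024, so a baseline may no longer be collectable. That changes the remedy, not the limit on interpretation.

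**Conclusion.** The point holds for attribution only. As planned, the weekly forms yield symptoms during consumption and cannot separate those that preceded the drink from those that began on it. Total symptom burden and severity during the four weeks, including grades 3 and 4, remain interpretable.

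The size of the pre-existing part cannot be computed, because the documents give no background rate. Under assumed rates of 10% to 30% and no beverage effect, 1 to 3 of 10 women would be expected to report a symptom, so a non-zero count by itself says little about cause. The textual finding rests on the forms and visits as the protocol describes them; the illustrations rest on the assumed rates and on independence between women and, in Step 3, between weeks. This is an inexpensive improvement to the design, not a defect that invalidates the pilot.

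**What to change.** **If enrolment is open.** Have each woman complete the same 0-4 form at the existing pre-dose visit, covering the preceding week. Report symptom prevalence and grade for the baseline week beside each of weeks 1 to 4, one week against one week, with each woman's change from baseline. Give counts as x/n with exact 95% confidence intervals, and keep the comparison descriptive. Do not use new or worse in any of four weeks against a single baseline week as the attributable count, because intermittent symptoms would inflate it.

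**If data collection is complete.** Report symptoms during consumption, and remove the causal reading from the heading of section 3.3.4 and from the Introduction.

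**Cost.** In the first case, 10 short forms are added to the 40 weekly ones (10 women × 4 weeks), with no extra visit. In the second, only wording changes. Change with advancing gestation, unrelated new onset and n = 10 would still limit attribution, and the report should say so.

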3.1. Ethical considerations

This research project complies with the International Ethical Guidelines for Research Related to Human Health, developed by the Council for International Organizations of Medical Sciences (CIOMS) in collaboration with the WHO.

All participants in this trial received dignified treatment and were not discriminated against under any circumstances based on their ethnic or national origin, social or economic status, religion, opinions, or marital status, in accordance with the Federal Law to Prevent and Eliminate Discrimination. Participants were never recruited against their will, nor did they suffer any form of disapproval or retaliation if they decided not to participate or withdrew from the study. It was emphasized that participation was completely voluntary and that they could refuse to participate or withdraw from the research at any time if they so desired.

The results obtained were used solely by the research team. The privacy of the participants, as well as the confidentiality of their personal information, was protected. All collected samples were identified by the participant's initials and a consecutive number, and only the researchers had access to their personal information. This information was kept safe with their file and will not be disclosed or published at any time. The results may be published for scientific purposes, but personal and identifying data of the participants will not be disclosed at any time. The results obtained were analyzed using Past software through pairwise analysis to determine statistical differences between the indicators measured before and after treatment with a significance level of $P < 0.05$. Descriptive statistics with means, standard deviations, and percentages were also applied to characterize the group.

The researchers of this protocol declare that there is no conflict of interest and that the objective is to generate knowledge that allows us to evaluate the effect of a beverage with *H. sabdariffa*, which can be used in the prevention and/or treatment of hypertensive disorders associated with pregnancy, as well as to determine its degree of acceptability and tolerability.

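### Does the 0-4 tolerability scale need rewording because a symptom that disturbs only sleep, or only daily activities, has no explicit grade?

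*Protocol*

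**What the plan says.** Section 3.3.4 describes a self-completed weekly form taken from a cited tolerance study of an enteral formula: "Once a week for the 4 weeks of the trial, participants completed a gastrointestinal tolerability assessment form". It names seven symptoms: nausea, regurgitation, vomiting, constipation, diarrhea, flatulence and abdominal pain.

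The scale begins "0=absent symptom, 1=symptom present but not bothersome" and continues "2=annoying symptom but does not interfere with daily activities or sleep, 3=a symptom present and bothersome but does interfere with daily activities and sleep". Grade 4 is a symptom that requires medical attention. The form itself is not reproduced, and no other section restates the grades or says how to grade a symptom that disturbs only one of the two domains.

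The matching objective in section 2.2 is "Determine the tolerability of the beverage by the presence of gastrointestinal symptoms". Section 3.1 mentions degree as well ("as well as to determine its degree of acceptability and tolerability"), and section 3.3.5 repeats this almost word for word ("as well as to determine its degree of gastrointestinal acceptability and tolerability"). Both occur in the conflict-of-interest statement. On size, section 3 says "A 4-week phase I pilot trial was conducted in 10 women in their second trimester of pregnancy", while section 3.3.2 says at least ten were recruited.

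**The concern.** A grading scale should give every possible answer exactly one grade. Here the definition of grade 2 joins the two domains with *or* under a negative, so neither may be disturbed. The definition of grade 3 joins them with *and*, so both must be. A woman whose nausea troubles her by day but lets her sleep, or whose flatulence wakes her but leaves her day untouched, meets neither definition. Grade 1 is closed to her because the symptom is bothersome, and grade 4 is closed unless medical attention is required.

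The women complete the form themselves, and the Protocol describes no assessor who would apply a common rule. Two women with the same symptom could therefore record different grades. As the scale is described, only the chosen grade is kept, so the analysis could not sort such entries afterwards. What would be at stake is the reliability of the split between grades 2 and 3, and with it any statement about how severe the symptoms were.

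**Working it through.** The Protocol gives no figure to reproduce here. The check is one of coverage, followed by a count of what the gap could alter.

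**Step 1: coverage.** Take a symptom that is bothersome and does not require medical attention. Let A mean that it disturbs daily activities and S that it disturbs sleep. From section 3.3.4, grade 2 is *not A and not S*; grade 3 is *A and S*.

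| A | S | Grade as worded | Grade if *and* in grade 3 is read as *and/or* |
|---|---|---|---|
| no | no | 2 | 2 |
| no | yes | none | 3 |
| yes | no | none | 3 |
| yes | yes | 3 | 3 |

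As worded, 2 of 4 combinations have a grade and 2 have none. With the looser reading all 4 have exactly one. The gap in the text is real, but it is a count of logical cells and says nothing about how often they occur.

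**Step 2: where an uncovered entry would go.** Grade 2 excludes any interference, so both uncovered rows contradict its definition outright. For grade 3 they satisfy the contrast the scale draws (the symptom interferes) and miss only the word *and*. On an ordered scale the nearest grade is 3.

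**Step 3: number of entries.** Seven symptoms (section 3.3.4) × 4 weekly forms × 10 women (section 3) = 280 if every form is complete. With the six symptoms listed in the Introduction, which omits abdominal pain, it is 6 × 4 × 10 = 240. Neither is a firm ceiling, because section 3.3.2 allows more than ten women. The Protocol gives no symptom rate, so the number in the gap could be zero.

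**Step 4: effect on what could be reported.** Suppose one uncovered entry is recorded as 2 instead of 3.

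- Count with the symptom present (grade ≥ 1): change 0, since 2 and 3 both count.
- Count at grade ≥ 2: change 0, for the same reason.
- Count at grade ≥ 3: change 1. For one symptom in one week among 10 women this is 1/10, or 10 percentage points.
- Mean grade for that symptom and week: change (3 − 2)/10 = 0.1.

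**Step 5: which of these the Protocol uses.** Section 2.2 uses the first. The last two would matter only if the Protocol set a criterion at grade 3 or an analysis of mean grade. It does neither: section 3.1 gives paired before-and-after comparisons of the measured indicators, plus means, standard deviations and percentages to characterize the group.

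**The case for a change.** The best case for changing the plan has three parts.

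First, the defect is in the Protocol's own text and arises when the data are collected, so it cannot be left to an analysis plan. The textual part of this stands. The claim that the data cannot be sorted afterwards holds only if the form the women filled in carries the same wording, and that form is not shown. There are signs of loose translation: grade 3 uses a *but* that makes no sense, grades 2 and 3 use different words for what seems the same level of annoyance, and section 3.3.3 uses *attachment* where adherence is meant. One conjunction in such a passage is weak evidence about the instrument itself.

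Second, the Protocol speaks of the degree of tolerability, and the grades look like its measure of degree. This carries little weight. The word occurs in this sense only in the conflict-of-interest paragraph, not in the general or specific objectives, and there it covers acceptability as well. Degree could also be described by how many symptoms occurred and for how many weeks, without the split.

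Third, the Introduction says the pilot is meant to reduce errors in later studies and prepare a randomized trial, so flaws in its instruments should be caught now. That is a fair reason to check the wording before any reuse. But the Protocol does not say that the later trial will use this form. The present study is reported in the past tense, so rewording could not regrade its entries, and it might depart from the cited form.

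**Conclusion.** The observation is correct as a reading of section 3.3.4, but it is a slip of wording and calls for no change to the plan. Two of four combinations lack an explicit grade. The tolerability objective in section 2.2 rests on presence, and on that measure, as at grade 2 or above, the effect is exactly zero. Only the boundary between grades 2 and 3 can move, by one count per affected entry. Nothing in the Protocol depends on that boundary, and a sensible respondent or analyst would put such a symptom at grade 3 because grade 2 excludes it.

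This rests on three assumptions: tolerability is reported by presence, as section 2.2 states; nobody treats the split between 2 and 3 as a result in its own right in a group of about ten women; and an uncovered symptom is recorded as 2 or 3, not left blank. If a report did draw a conclusion from grade 3 alone, the ambiguity would deserve a caveat there. That would be a matter for the report, not a fault that the plan must repair.
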